7.10. Week 16 (\pm 3 Days) Transition to Maintenance Period

- Administer the DLQI/CDLQI, and EQ-5D
- Administer the PROMIS measures
- Collect ACQ-5 for patients with comorbid asthma
- Complete the following assessments: IGA, BSA, EASI and SCORAD
- Perform a complete physical examination, including height and weight
- Review and record AEs and update concomitant medication and procedure/therapy information
- Review compliance report on the eDiary, confirm moisturizer use and remind patient to record the following: Pruritus and Sleep-Loss (daily), and POEM (weekly)
- Measure vital signs
- Draw pre-dose blood samples for laboratory tests, PK and ADA testing
- Collect a urine sample for urinalysis
- Conduct urine pregnancy test (WOCBP only)
- Re-randomize the patient to the Maintenance Period
- Train the patient to self-administer study drug
- Administer one injection and observe the patient self-injecting
- Dispense study drug for Week 18 injections

Sites collecting photos will also:

- Obtain a photograph of the target lesion

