
Other Secondary Endpoints Specific for Maintenance Period:
 
 Percentage of patients from those re-randomized having achieved EASI-75 at Week 16 who continue to exhibit EASI-75 at Week 52 (EASI-75 calculated relative to baseline EASI score) Percentage of patients from those re-randomized having achieved IGA 0 or 1 and a ≥ 2-point improvement from Baseline at Week 16 who continue to exhibit an IGA 0 or 1 and a ≥ 2-point improvement from Baseline at Week 52 Time to loss of EASI-50 in the subset of patients who were re-randomized at Week 16 (EASI-50 calculated relative to baseline EASI score) Time to loss of EASI-75 in the subset of patients who were re-randomized and achieved EASI-75 at Week 16 (EASI-75 calculated relative to baseline EASI score) Time to loss of IGA response, ie, developing an IGA score ≥ 2 with 2 points deterioration of achieved IGA response at Week 16, in the subset of patients who were re-randomized and achieved IGA 0 or 1 and a ≥ 2-point improvement from Baseline at Week 16 	
Major Secondary Endpoints Specific for Maintenance Period:
 
 Percentage of patients from those re-randomized having achieved EASI-75 at Week 16 who continue to exhibit EASI-75 at Week 52 (EASI-75 calculated relative to baseline EASI score) Percentage of patients from those re-randomized having achieved IGA 0 or 1 and a ≥ 2-point improvement from Baseline at Week 16 who continue to exhibit an IGA 0 or 1 and a ≥ 2-point improvement from Baseline at Week 52 Percentage of patients from those with a Pruritus NRS of ≥ 4-points at baseline re-randomized having achieved ≥ 4-point reduction from baseline at Week 16 who continue to exhibit ≥ 4-point reduction from baseline at Week 52 Percentage change in EASI score from Baseline at Week 52 in the subset of patients who were re-randomized at Week 16 
Other Secondary Endpoints Specific for Maintenance Period:
 
 Percentage change in SCORAD (having achieved EASI-75 at Week 16) from baseline at Week 52 Percentage of patients from those with a Pruritus NRS of ≥ 5-points at baseline re-randomized having achieved ≥ 4-point reduction from baseline at Week 16 who continue to exhibit ≥ 4-point reduction from baseline at Week 52 Time to loss of EASI-50 in the subset of patients who were re-randomized at Week 16 (EASI-50 calculated relative to baseline EASI score) Time to loss of EASI-75 in the subset of patients who were re-randomized and achieved EASI-75 at Week 16 (EASI-75 calculated relative to baseline EASI score) Time to loss of IGA response, ie, developing an IGA score ≥ 2 with 2 points deterioration of achieved IGA response at Week 16, in the subset of patients who were re-randomized and achieved IGA 0 or 1 and a ≥ 2-point improvement from Baseline at Week 16

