6.1.3. General Considerations for Analyses During Maintenance Period

Maintenance Period starts at the first injection of study treatment at Week 16 and ends on the date of Week 52 or the ETV (between Weeks 16 and 52) unless specified otherwise.

For the efficacy and health outcome analyses, baseline is defined as the last available value before the first injection in Induction Period and, in most cases, will be the value recorded at Baseline Visit (Day 1).

Unless otherwise specified, efficacy and health outcome scores at Week 16 prior to entering Maintenance Period will be presented for the visit wise reports for Maintenance Period.

Unless specified otherwise, for the safety analyses during Maintenance Period, baseline is defined as the last available value before first injection in Maintenance Period. In most cases, this will be the measure recorded at Week 16. For TEAEs, baseline is the events ongoing just prior to the first injection of the study drug injection at Week 16.

For patients in the Modified Maintenance Primary Population, Modified Maintenance Secondary Population, Maintenance Primary Population, and Maintenance Secondary Population who met escape criteria (EASI-50 nonresponse) and escaped to lebrikizumab 250 mg Q2W at Weeks 24, 32, 40 and 48, only data in the Maintenance Blinded Period (up to the time of escape) will be included in both efficacy and safety analyses.

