6.1.3.1. Modified Maintenance Primary and Maintenance Primary Populations

Unless otherwise specified, treatment comparisons of categorical efficacy and health outcomes variables will be analyzed using CMH test with treatment group and covariates as mentioned in Section 6.3 in the model. The CMH p-value will be reported, and the CMH adjusted odds ratio along with the 95% two-sided asymptotic (ie, not continuity corrected) CIs.

Each continuous efficacy and health outcomes measure score, change from baseline and percent improvement from baseline will be summarized by treatment group at all scheduled visits during Maintenance Period including Week 52, using descriptive statistics (n, mean, standard deviation (SD), median, minimum and maximum).

Treatment comparisons for continuous efficacy and health outcome variables will be made using ANCOVA model as specified.

When the ANCOVA is used, the model will include treatment, baseline value and covariates as mentioned in Section 6.3. The ANCOVA analysis will be conducted as described in Section 6.1.2.

The KM product limit method will be used to estimate the survival for time to event analyses (eg, time to loss of IGA response or time to loss of EASI-50 or time to loss of EASI-75). The stratified log-rank test will be performed with treatment group and covariates as mentioned in Section 6.3 in the model. A KM plot of the time to event by treatment group may be provided.

Unless specified otherwise, Fisher's exact test will be used for AEs and other categorical safety measures. Odds ratios will be created with lebrikizumab treatment as the numerator and placebo as the denominator. Continuous vital sign and laboratory values will be analyzed by an ANCOVA model with treatment and baseline value as independent variables.

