6.2.2.1. Maintenance Primary Estimand (Hybrid)

The maintenance primary estimand is a hybrid estimand representing the clinical question of interest: what is the difference between treatment conditions, ie, Lebrikizumab vs Placebo, in the target patient population, in successful responses or means after 52 weeks achieved without use of systemic rescue medication, without transferring to escape arm, if topical rescue medication were not available and if all patients continued with treatment except those who discontinued due to lack of efficacy?

The maintenance primary estimand is described by the following attributes:

- Population: Modified Maintenance Primary Population as described in Section 6.1.1.
- Endpoint: apply to all major and other secondary endpoints for Maintenance Period
- How to account for intercurrent events (ICEs)
 - Subjects who require any use of systemic rescue medication, discontinue treatment due to lack of efficacy after week 16, or transfer to escape arm will be

considered as treatment failures, ie, non-responder, after the ICEs. Therefore, composite strategy is used for these types of ICEs.

- b. For subjects who require any use of topical rescue medication, a hypothetical strategy will be used to estimate what the treatment effect would have been if subjects continued with treatment. Therefore, hypothetical strategy is used for these types of ICEs.
- c. For subjects who discontinue treatment due to reasons other than lack of efficacy after week 16, a hypothetical strategy will be used to estimate what the treatment effect would have been if subjects continued with treatment. Therefore, hypothetical strategy is used for these types of ICEs.

D. Population-level summary: difference in response proportions or means between treatment conditions

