6.3. Adjustments for Covariates

Unless otherwise specified, the statistical analysis models for the Induction Period efficacy and health outcome analysis will include the following stratification factors for Baseline randomization: geographic region (US versus EU versus rest of world), age (adolescent patients 12 to <18 versus adults ≥18 years) and baseline disease severity (IGA 3 versus 4).

The statistical analysis models for the Modified Maintenance Primary Population (Maintenance Blinded Period) efficacy and health outcome analysis will include geographic region (US versus EU versus rest of world). Below are the country allocations within each geographic region.

Below are the country allocations within each geographic region.

Table KGAC.6.5. Geographic Regions for Statistical Analysis

Geographic Region	Country or Countries
US	United States
Europe	Bulgaria, Germany, Ukraine
Rest of world	Canada, Mexico, Singapore, Taiwan

In general, when an MMRM is to be used for analyses, baseline value and baseline-by-visit interactions will be included as covariates; when an ANCOVA is to be used for analyses, baseline value will be included as a covariate.

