6.4.2. Handling of Dropouts or Missing Data for Maintenance Period

For maintenance efficacy analysis relative to the maintenance primary estimand, the method of handling missing data including those as a result of intercurrent events will be Markov Chain Monte Carlo Multiple Imputation (MCMC-MI). The description of maintenance MCMC-MI method can be found in Section 6.4.2.1.

MCMC-MI will also be used to handle missing data relative to the maintenance supportive estimand (Hybrid) as described in Section 6.4.2.1.

For efficacy analysis relative to the maintenance supportive estimand for categorical endpoints (Composite), missing data including those as a result of intercurrent events will be imputed as non-responder. The description of maintenance non-responder imputation (NRI) can be found in Section 6.4.2.2.

For efficacy analysis relative to the maintenance supportive estimand for continuous endpoints (Hypothetical), missing data including those as a result of intercurrent events will be imputed using Last Observation Carried Forward (LOCF). The description of maintenance LOCF can be found in Section 6.4.2.3.

Table KGAC.6.9 describes the planned imputation methods for efficacy and health outcome endpoints for Maintenance Period.

Table KGAC.6.9. Imputation Techniques for Various Variables During Maintenance Period

Type of Endpoints	Efficacy and Health Outcome Endpoints	Estimand (Analysis strategy for Intercurrent Events)	Missing Data Imputation Method (Analysis Method)
Categorical	IGA, EASI, and Pruritus NRS related categorical endpoints at pre-specified timepoints	Maintenance Primary Estimand (Hybrid)	MCMC-MI (CMH)
		Maintenance Supportive Estimand (Hybrid)	MCMC-MI (CMH)
		Maintenance Supportive Estimand (Composite)	NRI (CMH)
	Remaining categorical endpoints	Maintenance Supportive Estimand (Composite)	NRI (CMH)
Continuous	EASI percent change, Pruritus NRS percent change	Maintenance Primary Estimand (Hybrid)	MCMC-MI (ANCOVA)
		Maintenance Supportive Estimand (Hybrid)	MCMC-MI (ANCOVA)
		Maintenance Supportive Estimand (Hypothetical)	LOCF (ANCOVA)
	Remaining continuous endpoints	Maintenance Supportive Estimand (Hypothetical)	LOCF (ANCOVA)

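### Precision only, lowest priority: the maintenance ANCOVA for Week 52 percentage change in EASI omits the Week 16 EASI measured just before re-randomisation

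*SAP*

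**What the plan says.** SAP 6.1.3.1 sets the maintenance model: "When the ANCOVA is used, the model will include treatment, baseline value and covariates as mentioned in Section 6.3". Two other sections define its terms.

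- **Baseline.** SAP 6.1.3: "For the efficacy and health outcome analyses, baseline is defined as the last available value before the first injection in Induction Period". This is the Day 1 value in most cases, not the Week 16 value.
- **Covariates.** SAP 6.3 says that the mMPP "efficacy and health outcome analysis will include geographic region (US versus EU versus rest of world"). No other covariate is listed for this population.

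Protocol 7.10 lists, for the Week 16 visit, "Complete the following assessments: IGA, BSA, EASI and SCORAD" and, further down the same list, "Re-randomize the patient to the Maintenance Period". SAP 5.3 makes re-randomisation depend on the Week 16 IGA or EASI. A Week 16 EASI that precedes maintenance treatment should therefore exist for essentially every re-randomised patient.

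The endpoint concerned is an EMA major secondary in SAP Table KGAC.4.1: "Percentage change in EASI score from Baseline at Week 52 in the subset of patients who were re-randomized at Week 16". Table KGAC.6.12 assigns it ANCOVA with MCMC-MI in the mMPP. SAP 6.6.2 tests it seventh (Q2W) and eighth (Q4W), after six responder comparisons. Table KGAC.6.9 gives the continuous endpoints that use this method: "EASI percent change, Pruritus NRS percent change". The pruritus one is not in the alpha-controlled list.

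**The concern.** The maintenance comparison begins at re-randomisation. The value nearest to that point, on the same scale as the outcome, is the Week 16 EASI. The plan reports Week 16 scores in by-visit displays and may use them for imputation, since SAP 6.4.2.1 refers only to relevant baseline and post-baseline values. Neither use adjusts the treatment comparison.

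There is a structural reason to expect Week 16 EASI to be prognostic. Loss of EASI-50 leads to escape, and Table KGAC.6.4 sets escaped patients to baseline, which is 0% change. A patient who enters maintenance at 76% improvement is nearer that threshold than one at 98%. No stratification factor is stated for re-randomisation, and the placebo arm is small, so chance imbalance in depth of response would remain unadjusted. What is at stake is the precision of the two estimates against placebo, not their validity.

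**Working it through.** **1. The plan's own power figure.** SAP 5.2 gives more than 95% power for 96 versus 48 with a continuity-corrected chi-square test. For IGA 0/1 (34.7% vs 7.7%):

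- Pooled rate: (48 x 0.077 + 96 x 0.347)/144 = 0.257.
- Correction: (1/48 + 1/96)/2 = 0.0156.
- Null SE 0.0773; alternative SE 0.0620.
- z = (0.270 - 0.0156 - 1.96 x 0.0773)/0.0620 = 1.66, so power is 95.2%.

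For EASI-75 (48.0% vs 11.5%) the same formula gives 99.6%. The figure reproduces, but it concerns induction. The documents give no power, SD or effect for the maintenance EASI endpoint.

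**2. Projected mMPP size**, using the plan's 48.0% EASI-75 rate and before exclusions: 400 x 2/3 x 0.480 = 128. Split 2:2:1 this is 51.2 / 51.2 / 25.6 (Q2W / Q4W / placebo). Response rates of 40% to 55% would give 107 to 147 patients.

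**3. Chance imbalance.** The 95% range for the active-minus-placebo difference in Week 16 EASI is 1.96 x sqrt(1/51.2 + 1/25.6) = 0.47 SD either way. Any baseline variable would have the same range. It matters only if the variable is prognostic.

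**4. Analytic guide.** Adding one covariate with partial correlation r multiplies residual variance by (1 - r^2) x df/(df - 1), with df = 128 - 6 = 122.

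| r (assumed) | variance factor |
|---|---|
| 0 | 1.008 |
| 0.2 | 0.968 |
| 0.3 | 0.918 |
| 0.4 | 0.847 |

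**5. Simulation at 51/51/26.** All inputs here are assumptions:

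- All patients are EASI-75 responders. Baseline EASI is 16 plus a gamma(1.3, scale 10), capped at 72. Week 16 improvement is 75 + 25 x Beta(1.5, 1) per cent.
- Escape is 10% on each active arm and 25%, 35% or 50% on placebo. Log odds of escape rise by 0, 0.5, 0.8 or 1.2 per SD worse Week 16 response. Escapees are set to 0% change.
- Non-escapees improve by a mean of 89% (active) or 82% (placebo) at Week 52, with SD 12 and correlation 0.3 with Week 16 (0 at slope 0).
- Missing Week 52 values are none, 10% or 20% of non-escapees, completely at random. They are imputed within arm, with 25 datasets and Rubin's rules. There were 20,000 runs per cell without missing data and 1,600 with.

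Reduction in empirical variance of Q2W minus placebo when Week 16 EASI is added (%):

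| Placebo escape | Missing | slope 0 | 0.5 | 0.8 | 1.2 |
|---|---|---|---|---|---|
| 25% | none | -0.5 | 5.5 | 10.4 | 17.6 |
| 35% | none | -0.6 | 5.5 | 10.2 | 17.8 |
| 50% | none | -0.6 | 5.4 | 10.2 | 17.2 |
| 25% | 10% | -1.1 | 4.6 | 10.9 | 18.4 |
| 35% | 10% | -0.9 | 6.4 | 10.5 | 15.6 |
| 50% | 10% | -0.5 | 4.9 | 8.1 | 14.4 |
| 25% | 20% | -0.9 | 4.0 | 9.8 | 18.1 |
| 35% | 20% | -0.4 | 4.6 | 9.1 | 17.0 |
| 50% | 20% | -0.9 | 3.7 | 9.6 | 15.9 |

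For Q4W the reductions at slopes above 0 are 3.6% to 18.3%. A repeat without missing data gave about 5% to 21%.

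A differently built simulation (escape 5% active, 20% placebo) gave partial r of 0.15 to 0.43 and variance ratios of 0.99 to 0.83. The weakest gain arose when escape did not depend on Week 16. Mean estimates were nearly the same without and with the covariate (for example -17.65 and -17.58).

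**6. Power, given that both EASI-75 steps pass.** At step 7 the largest fall is 86.2% to 85.2% and the largest rise 89.2% to 91.1%. At step 8 they are 87.4% to 86.6% and 86.4% to 88.8%.

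**7. Calibration.** Without missing data, the model-based SE is 0.82 to 0.88 of the empirical SE without Week 16 EASI and 0.83 to 0.89 with it. Nominal 95% intervals cover about 90% to 93% either way, because the simulated arms have unequal variances.

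**The case against.** The strongest reply is that nothing here is an error. The plan's covariates match an endpoint defined as change from induction baseline, and protocol 9.3 asks only for the relevant baseline value. Choosing among valid covariates is partly preference. The benefit rests on quantities that the documents do not give, and the conditional power change spans zero. All of this stands, and it is why the point has the lowest priority.

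Two limits of the simulation also stand. SAP 6.2.2.1 says "For subjects who require any use of topical rescue medication, a hypothetical strategy will be used", and Table KGAC.6.4 implements this by setting such values to missing. Protocol 6.3 permits intermittent topical rescue in maintenance. Missingness could therefore be heavier than 10% to 20%, differ by arm and follow disease activity, whereas only completely random missingness was tried. In addition, only EASI-75 responders were simulated, although IGA 0 or 1 alone qualifies for re-randomisation. Selecting responders narrows the Week 16 range, which could put the true gain near the low end.

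A reader might infer that the covariate buys a tighter confidence interval. The simulated model-based interval is indeed 1.4% to 8.0% narrower when Week 16 is prognostic. Where coverage was checked it was already below nominal, with or without the covariate, so further narrowing is not a fair claim. Only the fall in empirical variance is.

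**Conclusion.** The observation is correct, and its consequence is limited to precision. The mMPP ANCOVA for Week 52 EASI percentage change leaves out a collected pre-randomisation value of the same measure. Adding it to a linear model leaves the difference-in-means estimand unchanged. The gain is about 4% to 18% of empirical variance under the assumed prognostic strengths and could be nearer 1% if escape is unrelated to Week 16 response. The loss is at most about 1% if Week 16 is not prognostic. These figures rest on assumed escape rates, SDs, associations and missingness.

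Three stronger readings are not supported.

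- **That the planned test is biased or uses the wrong baseline.** Re-randomisation protects the estimate, and the endpoint is deliberately measured from induction baseline. Only the maintenance safety analyses reset baseline to Week 16.
- **That the omission could decide the outcome.** Taken alone, the test could gain more power (80% to 83% at r = 0.3 by the analytic factor; up to about 8 points in simulation at the steepest slope). But step 7 is tested only after six binary comparisons succeed, and conditionally the change is about -1 to +2 points.
- **That the point reaches the six CMH steps.** They do not use this model.

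**What to change.** Before the maintenance assignment is unblinded:

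1. In SAP 6.1.3.1 and 6.3, state that the mMPP ANCOVA with MCMC-MI for EASI percentage change contains treatment, induction baseline EASI, Week 16 EASI score and region.
2. In SAP 6.4.2.1, state that the EASI imputation model includes Week 16 EASI, so that it matches the analysis model.
3. Apply the same to Pruritus NRS percentage change, taking any missing Week 16 weekly mean from the same imputed dataset.

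Leave the endpoint, the CMH steps and the LOCF ANCOVAs as they are. Under SAP 6.4.2.3 a missing Week 52 value may be the carried-forward Week 16 value itself, so that value should not also be a covariate there.

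The cost is about one degree of freedom, one rule for pruritus, and no new EASI data. The MI analysis and the supplementary LOCF analysis of EASI would then differ in one covariate as well as in missing-data handling. That should be noted wherever the two are compared.

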6.1.3.2. Modified Maintenance Secondary Population

The number and percentage of patients achieving or maintaining a categorical efficacy and health outcome responses will be summarized by treatment group for all scheduled visits, including Week 52.

Selected continuous secondary efficacy and health outcomes measure score and change from baseline (or percent improvement) will be summarized by treatment group at all scheduled visits during Maintenance Period, including Week 52 using descriptive statistics (n, mean, SD, median, minimum, and maximum). No inferential statistics will be provided for this population.

6.1.3.3. Modified Maintenance Escape Populations

For the Modified Maintenance W16 Escape Population, the number and percentage of patients achieving or maintaining a categorical efficacy and health outcome responses will be summarized by treatment group for all scheduled visits, including Week 52. Selected continuous secondary efficacy and health outcomes measure score and change from baseline (or percent improvement) will be summarized by treatment group at all scheduled visits during Maintenance Period, including Week 52 using descriptive statistics (n, mean, SD, median, minimum, and maximum). No inferential statistics will be provided for this population.

For the Modified Maintenance W24-48 Escape Population who were treated with lebrikizumab 250 mg Q2W following loss of response (EASI-50 nonresponse), the number and percentage of patients regaining EASI-50 response or achieving EASI-75 will be summarized every 4 weeks after lebrikizumab 250 mg Q2W treatment. No inferential statistics will be provided for this population.

6.1.4. General Considerations for Safety Analyses for Combined Induction and Maintenance Periods

Adverse event, exposure summary, and categorical laboratory/vital sign changes will be provided for the All Lebrikizumab Modified Safety Population and the All Lebrikizumab Safety Population during the Combined Induction and Maintenance Periods. For patients who were first exposed to lebrikizumab during Induction Period, the baseline for TEAE will utilize the baseline for Induction Period defined in Section 6.1.2; for patients who were first exposed to lebrikizumab during Maintenance Period, the baseline for TEAE will utilize the baseline for Maintenance Period defined in Section 6.1.3.

More details on baseline and postbaseline definitions can be found in the Compound Level Safety Standard.

6.1.5. General Considerations for Safety Analyses for Combined Induction and Maintenance Periods Plus Follow Up Period

Selective AE summaries will be provided for the All Lebrikizumab Modified Safety Population and the All Lebrikizumab Safety Population during the Combined Induction and Maintenance Periods plus Follow up Period. The baseline definition for this population is the same as Section 6.1.4. More details on baseline and postbaseline definitions can be found in the Compound Level Safety Standard.

